3.1.3 Definition of Baseline

Baseline is defined as Study Day 1. Subject with missing baseline value will be considered as missing and will be excluded from the analysis for the change from baseline endpoints.

3.1.4 *Summary Statistics*

In general, categorical data will generally be summarized with counts and percentages of subjects. The denominator used for the percentage calculation will be clearly defined.

Continuous data will generally be summarized with descriptive statistics including n (number of observations), mean, median, standard deviation, minimum, and maximum.

3.1.5 *Hypothesis Testing*

Corresponding with the primary efficacy objective of the study, the primary inference for hypothesis testing is the treatment difference between the combination of SL BUP/NAL SOC background therapy and the digital therapeutic OXD01, and SL BUP/NAL alone to reduce opioid use, as measured by the treatment success rate from Week 6 to Week 25. The hypothesis testing is based on a two-sided test with significance level at 0.05.

3.1.6 *Evaluation of Site Effect*

This is a multicenter study. Sites will not be pooled for any planned inferential analysis.

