3.4.2 Secondary Endpoints Analysis

The secondary objectives are to determine whether the combination of SL BUP/NAL SOC background therapy and the digital therapeutic OXD01 is superior to SL BUP/NAL alone with respect to the following variables. Note that the secondary objectives are listed in priority order for potential gatekeeping statistical approaches. The second test will only be conducted if the first test is statistically significant, and the following tests will only be conducted if the previous test is statistically significant.

The following secondary endpoints will be tested in a hierarchical fashion to protect the family-wise type I error:

- Cumulative response – The cumulative response rate from Week 6 to Week 25 of treatment. Response is defined as the presence of both a negative urine drug test for opioids and a self-report negative for illicit use of opioids at a study visit.

To compare the two treatment groups with respect to their cumulative distribution functions of the proportion of subjects responding, the Kolmogorov-Smirnov methodology will be used.

- Illicit use of opioids - The cumulative response rate from Week 6 to Week 25 of treatment with respect to the percentage of urine drug tests negative for opioids will be the primary metric for this variable. To compare the two treatment groups with respect to their cumulative distribution functions of the proportion of subjects responding, the Kolmogorov-Smirnov methodology will be used.
- Self-reports of illicit use of opioids - The cumulative response rate from Week 6 to Week 25 of treatment with respect to the percentage of self-reports negative for illicit use of opioids will be the primary metric for this variable. To compare the two treatment groups with respect to their cumulative distribution functions of the proportion of subjects responding with self-reports negative for illicit opioid use, the Kolmogorov- Smirnov methodology will be used.
- Percentage of subjects abstinent - Abstinence is defined as a subject having urine drug tests negative for opioids as well as self-reports negative for illicit use of opioids at Week

25. Each subject will be scored as abstinent or non-abstinent and the groups will be compared using a chi-squared test.

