- Proportion of subjects completing the study - A completer is defined as a participant who completed either the UDS or the self-report assessment at the Week 25 visit. The groups will be compared with respect to the proportion of completers using a chi-squared test.
- Clinical global impression - This will be evaluated in two ways
 - Score on the CGI-I scale at week 13 and Week 25
 - Change from baseline in the Clinical Global Impression-Severity score at Week 13 and Week 25

CGI scores will be evaluated using General Linear Model (GLM) methodology with treatment as categorical covariate. If substantial deviations from the model assumptions are observed, then supportive analyses such as non-parametric assessments including a Mann-Whitney U test will be performed.

- Opioid cravings - Change from baseline in the opioid craving score using the Opioid Craving VAS from Week 4 to Week 25. Opioid Craving scores will be evaluated using GLM methodology with treatment as categorical covariate. If substantial deviations from the model assumptions are observed, then supportive analyses such as non-parametric assessments including a Mann-Whitney U test will be performed.
- Use of illicit non-opioid drugs of abuse - The cumulative percentage of subjects with urine drug tests negative for illicit drugs of abuse (excluding opioids) plus self-reports negative for illicit drug use for the period from Week 6 to Week 25 will be evaluated using the Kolmogorov-Smirnoff methodology.
- Number of hospitalizations, emergency department visits, and overdoses, and the ability to resume work, school, or other productive activity. descriptive statistics (count and percentage) will be summarized by treatment.

3.4.3 *Exploratory Analysis*

- Percentage of subjects with longer abstinent – Longer abstinence is defined as a subject having urine drug tests negative for opioids as well as self-reports negative for illicit use of opioids at Week 22 – Week 25. Each subject will be scored as abstinent or non-abstinent and the groups will be compared using a chi-squared test.

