The Quantity-Frequency Index (QFI) is a self-assessment of the frequency and quantity of alcohol consumption over the previous 30 days. The QFI is comprised of the two questions and will be completed on study Day 1 and at the visit on Week 25.

Individual data listings of QFI will be presented for each subject and visit of collection.

3.5.6 *Timeline Followback Method – Drug and Alcohol Use*

The Timeline Followback Method – Drug and Alcohol Use (TLFB) is a self-assessment used to document recent use of opioids, other illicit drugs of abuse, and alcohol. A TLFB assessment will be completed on study Day 1, and at weekly visits while on study treatment. The TLFB is a closed Yes or No question of drug or alcohol use.

Individual data listings of TLFB – drugs and TLFB – alcohol will be presented for each subject and visit of collection, separately.

3.5.7 *Opioid Craving Visual Analog Scale*

Cravings for opioids will be assessed by the subject through the use of a VAS, where 0 mm represents “no cravings” and 100 mm represents “the most intensive craving I have ever had.” The baseline craving VAS assessment will be collected on study Day 1 and at the visit on Weeks 5, 9, 13, 17, 21 and 25.

Individual data listings of opioid craving VAS will be presented for each subject and visit of collection.

3.5.8 *Quick Inventory of Depression Symptoms (Self-Report)*

Symptoms of depression will be assessed by the subject using the Quick Inventory of Depression Symptoms Self-Report (QIDS-SR) at screening and at the visit on Week 25.

Individual data listings of QIDS-SR will be presented for each subject and visit of collection.

3.5.9 *Review Behavioral Health Therapies since The Previous Visit*

Subjects in behavioral health therapies since the previous visit, including 12-step programs, will be recorded at the visits on Weeks 1-5, 7, 9, 11, 13, 17, and 21 in eCRF.

Individual data listings of behavioral health since previous visit will be presented for each subject and visit of collection.

3.5.10 *Clinical Global Impression*

Clinical Global Impression (Severity) – Severity of opioid dependence will be assessed by the Investigator on study Day 1 and at the visit on Week 13 and Week 25 using the assessment scale (rate from 0 to 7).

Clinical Global Impression (Improvement) – Improvement in severity of opioid dependence from baseline (study Day 1) will be assessed by the Investigator at the visit on Week 13 and Week 25 using the assessment scale (rate from 0 to 7).

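### The models for change in craving VAS and CGI-S leave out the Day 1 score: a valid analysis, but less precise than the collected data allow

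*SAP*

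**What the plan says.** **Model.** For craving, SAP 3.4.2 says "Opioid Craving scores will be evaluated using GLM methodology with treatment as categorical covariate". For CGI it says "CGI scores will be evaluated using General Linear Model (GLM) methodology with treatment as categorical covariate". Protocol 11.4 asks only for a general linear model or a non-parametric analog and names no terms.

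**Day 1 data.** SAP 3.5.7 and Protocol 6.14 have the craving VAS "collected on study Day 1 and at the visit on Weeks 5, 9, 13, 17, 21 and 25". SAP 3.5.10 and Protocol 6.17 have CGI-S scored on Day 1, Week 13 and Week 25. SAP 3.1.3 adds: "Subject with missing baseline value will be considered as missing and will be excluded from the analysis for the change from baseline endpoints".

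**Hierarchy.** SAP 3.4.2 tests the secondary endpoints in listed order to protect the family-wise error: "the following tests will only be conducted if the previous test is statistically significant". CGI is sixth on the list and craving seventh.
- The CGI step holds four comparisons: "Score on the CGI-I scale at week 13 and Week 25", and change in CGI-S at the same two visits.
- The craving step is "Change from baseline in the opioid craving score using the Opioid Craving VAS from Week 4 to Week 25". No visit, average or model contrast is singled out, and no VAS is scheduled at Week 4.

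**The concern.** A change score uses the baseline, but in a fixed way: it subtracts the whole Day 1 value, as if the slope of follow-up on Day 1 were exactly 1. Where the true slope is below 1, this adds noise. Putting the Day 1 score in the model lets the data set the slope. Both endpoints have the Day 1 score on file for every subject who enters the change analysis, so any precision lost is lost for no saving. What is at stake is power on two secondary endpoints, together with an uncorrected chance imbalance at Day 1. The point does not extend to CGI-I, which has no Day 1 score of its own.

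There is also a smaller question. A gate that opens on significance needs one decision per step, and the CGI and craving steps do not say which result gives it.

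**Working it through.** **The plan's own figure.** Neither document gives an SD, effect size or power for craving or CGI. The only sizing is for the primary endpoint: about 200 per arm for 90% power, 12% against 25%. Exact two-sided Fisher power at 200 per arm is 90.4%, so that figure reproduces. Nothing below depends on it.

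**Inputs.** Two-sided 5% level (SAP 3.1.5 states it for the primary test and no other level is given). Assumed, not in the documents: correlation rho between Day 1 and follow-up of 0.3 to 0.7; ratio k of follow-up SD to Day 1 SD of 1, then 0.7 to 1.3.

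**Variance of the treatment effect**, in units of the Day 1 variance:
- change score, treatment only: k² + 1 - 2·rho·k
- with the Day 1 score: k²(1 - rho²)
- difference: (1 - rho·k)², never negative, so adjustment cannot lose in large samples; the gain vanishes when rho·k = 1.

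**Equal SDs (k = 1).** The ratio is (1 - rho²) / (2(1 - rho)) = (1 + rho)/2. Power of the planned model is Φ((1.96 + z)·√ratio - 1.96), with z = 0.842 or 1.282 for adjusted power of 80% or 90%.

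| rho | Variance ratio | Planned power when adjusted is 80% | Planned power when adjusted is 90% |
|---|---|---|---|
| 0.3 | 0.65 | 62% | 74% |
| 0.5 | 0.75 | 68% | 80% |
| 0.7 | 0.85 | 73% | 85% |

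Example for rho = 0.3: 2.802 × √0.65 = 2.259; 2.259 - 1.96 = 0.299; Φ(0.299) = 62%.

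**Unequal SDs.** The extremes of the assumed range are:
- k = 0.7, rho = 0.3: 0.49 × 0.91 / (0.49 + 1 - 0.42) = 0.446/1.07 = 0.42
- k = 1.3, rho = 0.7: 1.69 × 0.51 / (1.69 + 1 - 1.82) = 0.862/0.87 = 0.99

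**Validity.** In simulated null trials (6,000 per setting, 200 per arm; normal, skewed 0-100 and 7-point scores), type I error was 4.7-5.2% for treatment only and 4.7-5.3% with the Day 1 score. Neither model inflates error.

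**The gate.** Suppose, as one possible reading, that any single p < 0.05 opened the next step. With independent results, null error at the step would be 1 - 0.95⁴ = 18.5% for CGI and 1 - 0.95⁶ = 26.5% for craving. At a correlation of 0.9 between test statistics, simulation gives about 9% and 11%. The family-wise rate would pass 5% only if the chance of reaching the step exceeded 5% divided by those rates: 27-54% for CGI and 19-46% for craving, taking the step's null results as independent of the earlier gates. A fixed order, one named contrast or a rule that all must be significant stays at or below 5%.

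The choice also moves power. Assume 80% power at every visit, no missed visits, and change scores correlated 0.50 to 0.79 across visits. The craving step then passes 48-61% of the time if all six visits are required, 80% on one named visit, and 87-96% on the six-visit mean.

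**The case against.** The strongest reply is that the first part is a preference about efficiency. An unadjusted change-score comparison in a 1:1 randomized trial is unbiased, and the documents set no power target for craving or CGI-S, so no stated claim fails. The size of the gain also rests on a correlation and an SD ratio that the documents do not give, and the range ends at almost nothing. All of that stands. It limits the weight of the point but does not remove it: adjustment costs nothing here and cannot lose in large samples.

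A reader might infer that the treatment-only model biases the comparison or raises the false-positive rate. It does neither.

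A reader might also infer that the hierarchy as written carries an error of 9-19% at the CGI step or 11-26% at craving. The documents do not support that. Those figures need a rule that any significant result opens the gate. The SAP never states such a rule, and it would defeat the stated aim of protecting the family-wise error. For CGI, testing one by one in listed order is a natural reading and controls error. Both steps sit late in the list, and only one inferential step (non-opioid drugs) follows craving. The Week 4 wording is an editorial mismatch, since the Week 5 visit on Day 29 comes after four weeks of treatment.

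Finally, SAP 7 defers detail to programming specifications in a separate document that is not among those reviewed. It may name more model terms or a contrast, though a rule that decides significance belongs in the SAP.

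**Conclusion.** The first part holds as a loss of precision. Treatment is the only named term in the models for change in craving VAS and CGI-S, although the Day 1 score is collected and already required for entry to these analyses. With equal SDs and a correlation of 0.3 to 0.7, the planned model has 1.18 to 1.54 times the variance of the adjusted one (1/0.85 to 1/0.65). If the SDs differ by up to 30%, the benefit of adjusting may be larger or close to nil. These sizes are assumptions, and the trial's own data would settle them.

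The second part is an unstated rule, not an error shown in the plan. The SAP does not say which craving result decides its step, and the order for CGI is left to be inferred. Writing it down removes any room to choose after results are seen. The primary endpoint is not affected by either part.

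**What to change.** 1. In SAP 3.4.2, add the Day 1 craving VAS as a covariate in the GLM for change in craving, and the Day 1 CGI-S in the GLM for change in CGI-S. The cost is one term per model; no data or subjects are lost.
2. Before database lock, name the craving contrast that decides the step, either one visit or the mean over Weeks 5 to 25, and reconcile the Week 4 wording with the Week 5 VAS visit. A period mean needs a stated rule for missed visits.
3. Confirm the order of the four CGI comparisons, or the rule that combines them. Requiring all four to be significant lowers the chance of passing the step; a fixed order or one named comparison avoids that.

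Items 2 and 3 cost a few sentences.

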#### 6.14 Opioid Craving Visual Analog Scale

Cravings for opioids will be assessed by the subject through the use of a VAS, where 0 mm represents “no cravings” and 100 mm represents “the most intensive craving I have ever had.” The baseline craving VAS assessment will be collected on study Day 1 and at the visit on Weeks 5, 9, 13, 17, 21 and 25 (Appendix F).

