3.4 Efficacy Assessment

Efficacy data will be summarized by randomized treatment based on the FA Population. The primary efficacy endpoint will also be summarized based on the mFA Population.

3.4.1 *Primary Endpoints Analysis*

The primary objective of the study is to determine whether the combination of SL BUP/NAL SOC background therapy and the digital therapeutic OXD01 is superior to SL BUP/NAL alone to reduce opioid use, as measured by the treatment success rate. Treatment success is defined as the subject having $\geq 80\%$ of urine drug tests negative for opioids plus $\geq 80\%$ of self-reports negative for illicit opioid use (from the TLFB interview at the same visit) from Week 6 to Week 25. Each subject will be evaluated as a success or failure for this metric and the proportion of subjects in each group demonstrating $\geq 80\%$ of urine drug tests negative for opioids plus negative self-reports for illicit opioid use (from the TLFB interview) will be tested using chi-squared test. Count and percentage of the subjects with treatment success will be summarized by treatment based on FA Population.

If the subject withdrew the study, then the urine drug tests for opioids and self-reports for illicit opioid use after withdrawal will be imputed as positive. If the subject completed the study with any missing visit, then the urine drug tests for opioids and self-reports for illicit opioid use for the missing visit will be imputed as positive.

Sensitivity analysis 1

As supportive analyses to the primary analysis for the primary endpoint, sub-group analysis using a similar chi-squared test as described above will be repeated for the following factors:

- Percentage of subjects meeting primary endpoint by reported compliance rate or who achieved greater than 80% completion of the visits during Week 6 to Week 25
- Subjects who took the dose of buprenorphine versus retention.
 - Target dose or lower: ≤ 16 mg buprenorphine for Suboxone or equivalent formulation; or ≤ 11.4 mg Zubsolv
 - Higher dose than target dose: > 16 mg buprenorphine for Suboxone or equivalent formulation; or > 11.4 mg Zubsolv
- Subjects who received additional behavioral health services

Sensitivity analysis 2

As supportive analyses, the primary endpoint and key secondary endpoints will be performed using the similar statistical methods based on mFA Population.

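### Craving and CGI get a treatment-only model with no missing-data rule; a repeated-measures model would use leavers' earlier scores, and is valid if dropout depends on observed scores

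*SAP*

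**What the plan says.** **Models.** SAP 3.4.2: "CGI scores will be evaluated using General Linear Model (GLM) methodology with treatment as categorical covariate", and "Opioid Craving scores will be evaluated using GLM methodology with treatment as categorical covariate". No visit, subject or baseline term is named. A Mann-Whitney test is offered as support if model assumptions fail.

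**Endpoint and schedule.** SAP 3.4.2 defines the craving endpoint as "Change from baseline in the opioid craving score using the Opioid Craving VAS from Week 4 to Week 25". Protocol 6.14 says that craving "will be collected on study Day 1 and at the visit on Weeks 5, 9, 13, 17, 21 and 25", so there are six post-baseline ratings and none is scheduled at Week 4. Under SAP 3.5.10, CGI-S is "assessed by the Investigator on study Day 1 and at the visit on Week 13 and Week 25", while CGI-I "will be assessed by the Investigator at the visit on Week 13 and Week 25" and has no baseline. Protocol Table 2 also schedules all three at early termination, and SAP 3.1.2 maps those visits to windows (Week 13 is Days 82-88; Week 25 is Day 166 onward).

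**Missing data.** SAP 3.4.1 says that "urine drug tests for opioids and self-reports for illicit opioid use after withdrawal will be imputed as positive" and treats a missed visit the same way; it names only those two measures. SAP 3.1.3 excludes subjects without a baseline from change-from-baseline analyses. Neither covers a missing post-baseline craving or CGI score, although Protocol 11 says the SAP will contain the missing-data procedure.

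**Order of testing.** SAP 3.4.2 tests the secondary endpoints in sequence, each only if the one before it is significant. Completion is fifth, CGI sixth, craving seventh.

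**The concern.** The stated model does not say which craving visit or summary is tested, nor what becomes of subjects without that score. The natural reading of a treatment-only GLM is an analysis of whoever has a score at the visit. A subject who leaves after Week 21 has five post-baseline craving ratings, and none of them would inform a Week 25 comparison.

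Selection is the larger worry. Treatment failure and loss to follow-up are listed discontinuation reasons (Protocol 4.4), and leavers are not replaced. CGI and craving are formally tested only when completion has already differed significantly between arms. Completion is defined by a Week 25 urine test or self-report, so it is not identical to having a Week 25 craving score, but it should track it closely. The comparison of attenders therefore counts as a formal test just when the two groups of attenders have been selected to different degrees.

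**Working it through.** **1. The plan's own figure.** The only sizing calculation is for the primary endpoint: 12% vs 25%, two-sided 0.05, 90% power.

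n = [1.960·√(2·0.185·0.815) + 1.282·√(0.12·0.88 + 0.25·0.75)]² / 0.13² = 186 per arm without continuity correction, and 201 with it. Exact Fisher power at 200 per arm is 90.4%. The stated 200 reproduces, but says nothing about craving or CGI.

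**2. Ratings left unused by a Week 25 comparison.**
- Craving: Weeks 5, 9, 13, 17 and 21, so up to five per leaver.
- CGI-S and CGI-I: Week 13 only, so at most one scheduled rating, and none for a subject who leaves before Week 13.

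**3. Loss of precision from analysing attenders only.** With dropout d (assumed), SE multiplier = √(1/(1−d)). The difference detectable with 80% power, in SD units, is (1.960 + 0.842)·√(2/m) with m = 200(1−d).

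| d | m per arm | SE multiplier | Detectable difference (SD) |
|---|---|---|---|
| 0% | 200 | 1.00 | 0.28 |
| 20% | 160 | 1.12 | 0.31 |
| 40% | 120 | 1.29 | 0.36 |
| 60% | 80 | 1.58 | 0.44 |

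A repeated-measures model recovers only part of this.

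**4. Where the precision gain comes from.** Simulation at 200 per arm with assumed inputs: subject SD 16, AR(1) residual SD 16, true difference 8 mm, dropout driven by the last score. One case, with autocorrelation 0.63 and 40%/36% dropout:
- treatment-only GLM on change: SE 2.78
- the same subjects with baseline as covariate: SE 2.48, which is 1 − 2.48/2.78 = 11% smaller
- repeated measures with baseline: SE 2.41, which is 1 − 2.41/2.78 = 13% smaller

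The baseline term supplies (2.78 − 2.48)/(2.78 − 2.41) = 0.30/0.37 = 81% of the gain. Across scenarios its share was 59-87%. The earlier visits add 1 − 2.41/2.48 = 3% here. With these SDs the total reduction under observed-score dropout was 12-17%. A second set (SD 25, serial correlation 0.7, 38-53% missing at Week 25), which does not separate the two sources, gave 9-14% for craving and 4-10% for a measure with two post-baseline visits, like CGI-S.

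**5. Bias.** Second set, 600 trials per scenario, dropout depending on the score more strongly in the control arm. Entries are bias in the Week 25 difference, OXD01 minus control; negative favours OXD01. The two-visit measure is on the same SD-25 scale, not in CGI points.

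| Dropout depends on | Measure | Treatment-only GLM | Repeated measures |
|---|---|---|---|
| last observed score (MAR) | craving | −2.4 to −2.8 | within 0.25 of zero |
| last observed score (MAR) | two-visit | −2.6 to −2.7 | within 0.25 of zero |
| unseen current score (MNAR) | craving | +0.3 to +0.9 | +2.3 to +2.6 |
| unseen current score (MNAR) | two-visit | +1.0 to +1.7 | +2.8 to +3.3 |

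Monte Carlo error for craving is about 4.4/√600 = 0.18. With the SDs of step 4, GLM bias under MAR with dropout differing by arm was 0.4-2.1 mm. Where dropout was unrelated to the score, or related to it equally in both arms, both methods in the second set were within about 0.6 of the truth.

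The smaller GLM bias under MNAR is not robustness. Control attenders have low Week 25 scores but also low baselines, and in a change score the two errors partly cancel.

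**The case against.** The case for leaving the plan largely alone has real force.

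- **A reader might infer that repeated measures removes dropout bias.** It does so only if dropout is explained by observed scores. With treatment failure and loss to follow-up among the discontinuation reasons, dependence on unseen scores is plausible, and step 5 shows the model can then be the more biased of the two. This stands.
- **A reader might infer that everyone who leaves early is dropped.** The documents do not say so. An early-termination rating inside the Week 13 window, or from Day 166, counts for that visit, and Week 13 CGI has its own analysis. The rescue is limited: CGI ratings mapped elsewhere reach no analysed visit, and SAP 3.1.1 counts days from first device use, which control subjects do not have.
- **A reader might infer that the planned GLM is biased whenever craving drives dropout.** In the step 4 set-up it averaged 7.84-8.09 mm against a true 8 at roughly 40%/36% and 56%/50% dropout. Under observed-score dropout, material bias appeared only when dropout operated differently in the two arms. A shortfall to 7.1 mm (12%) can be produced, but by a baseline-adjusted analysis of completers, which the SAP does not plan.
- **A reader might credit the earlier visits with the whole power gain.** Most of it is baseline adjustment, available without repeated measures.
- **A reader might infer an inflated type I error.** Six visits entered as independent rows, with within-subject correlation 0.3-0.6, give a design effect of 1 + 5 × 0.3 = 2.5 to 1 + 5 × 0.6 = 4.0 and a type I error of 22-33%. No text says rows would be entered that way, and the figure assumes all six ratings for everyone.

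None of this supplies a missing-data rule or names the craving test.

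**Conclusion.** The concern holds in a limited form. The SAP gives craving and CGI a treatment-only model, no rule for missing post-baseline scores and, for craving, no named visit. That only observed scores enter is inferred from this silence, not written.

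A repeated-measures model is a better main analysis: it uses the leavers' ratings and replaces an unstated assumption with a stated one. For craving the expected gain is a standard error about 9-17% smaller, of which the earlier visits contribute only a few percent. If dropout differs by arm and depends on observed scores, a bias of roughly 0.4-2.8 mm falls to near zero. For CGI the gain is smaller. Under MNAR bias remains and can exceed the GLM's, so the model needs a sensitivity analysis beside it.

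These sizes rest on assumed SDs, correlations, 200 per arm and about 40-60% dropout; the magnitudes and signs would move with other inputs. The primary endpoint is untouched, and the affected tests are sixth and seventh in the sequence.

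**What to change.** In SAP 3.4.2:

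1. Name Week 25 as the tested craving visit.
2. Analyse craving and CGI-S with a mixed model for repeated measures: arm, visit, arm-by-visit, baseline, and unstructured within-subject covariance, in all randomized subjects with at least one post-baseline score. Use the same model without baseline for CGI-I.
3. State that the model is valid if dropout depends on observed scores (MAR).
4. Add a delta-adjusted or tipping-point sensitivity analysis for dropout that depends on unseen scores.
5. State how early-termination ratings enter, including those mapped to a week with no scheduled craving or CGI rating, and give control subjects a reference day for the windows.

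The cost is SAP wording, one standard procedure and some extra analysis work; no new data are collected. The price in assumptions is that the main estimate relies on MAR.
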